5.4 Statistical Analysis Methods

5.4.1 Difference in Percentages

The difference in percentage, given by the difference between the proportion of subjects in the vaccine group, p_2 , with the event and placebo group, p_1 , with the event is calculated using the following formula:

$$\text{Difference in percentage} = (p_2 - p_1) * 100 = \left(\frac{E_2}{n_2} - \frac{E_1}{n_1} \right) * 100 \quad (1)$$

where E_1 and E_2 are the number of events in the placebo and vaccine groups respectively, and n_1 and n_2 are the number of subjects in the placebo and vaccine groups respectively with a valid assessment.

The 95% confidence intervals for the differences in percentages will be computed using the Miettinen and Nurminen (MN) [2] method. The following formula is used for the MN CI:

$$\text{MN CI} = \left((\hat{p}_2 - \hat{p}_1) \pm Z_{1-\frac{\alpha}{2}} \sqrt{\lambda \left(\frac{\tilde{p}_2(1-\tilde{p}_2)}{n_2} + \frac{\tilde{p}_1(1-\tilde{p}_1)}{n_1} \right)} \right) * 100 \quad (2)$$

where \tilde{p}_1 and \tilde{p}_2 are the maximum likelihood estimators for p_1 and p_2 under the null hypothesis that $p_1 - p_2 = 0$ and $\lambda = \frac{n_1+n_2}{n_1+n_2-1}$ and α is the selected level of significance. All confidence intervals for the difference in percentages outlined in this SAP will be two-sided 95% confidence intervals, i.e. with $\alpha = 0.05$.

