5.4.4 Geometric Mean Fold Rise

The geometric mean fold rise (GMFR) is given by taking the mean of the natural logarithm of the fold increases (**Section 5.3.2.1**). Therefore for the fold increases fi_1, \dots, fi_n , the GMFR is

$$GMFR = \exp \sum_{j=1}^n (\log\{fi_j\} / n).$$

Which is equivalent to

$$GMFR = \frac{GM_4}{GM_2}$$

where GM_2 is the geometric mean at Visit 2 and GM_4 is the geometric mean at Visit 4.

The 95% confidence interval for GMFR will be calculated using the same method as the 95% CI for GM (outlined in **Section 5.4.2**) but using the log of the fold rises rather than the log of concentrations.

6 Sample Size

This trial is designed to be descriptive, and therefore the sample size was not determined based on formal statistical power calculations. The planned number of subjects is approximately 400, with 200 receiving HIL-214 and routine childhood vaccines and 200 receiving Placebo and routine childhood vaccines.

7 General Considerations

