For continuous variables the ANOVA models will include all non-missing data for the parameter of interest and then the weights to account for the missing data. For binary data the proportions, which will be calculated on the complete cases data, will be reweighted, and the reweighted proportions will be used in the calculation of the confidence intervals. Therefore, in Equation (1) in [Section 5.4.1](#) will be calculated as the following:

$$\text{Difference in percentage} = (p_2 - p_1) * 100 = \left(\frac{(E_3|t_3 \times w_3) + (E_4|t_4 \times w_4)}{N_2} - \frac{(E_1|t_1 \times w_1) + (E_2|t_2 \times w_2)}{N_1} \right) * 100$$

Where E_i are the number of observed events in each category t_i and N_1 and N_2 are the number of subjects in the analysis set in the placebo and vaccine groups respectively. If all observed cases are positive in both vaccine groups, then the difference will be set to 0.

Equation (2) in [Section 5.4.1](#) will be calculated as the following:

$$\text{MN CI} = \left((\hat{p}_2 - \hat{p}_1) \pm Z_{1-\frac{\alpha}{2}} \sqrt{\lambda \left(\frac{\tilde{p}_2(1-\tilde{p}_2)}{N_2} + \frac{\tilde{p}_1(1-\tilde{p}_1)}{N_1} \right)} \right) * 100$$

Where $\lambda = \frac{N_1+N_2}{N_1+N_2-1}$.

If all observed cases are positive in both vaccine groups confidence intervals will not be calculated.

In the tables the number of events will be rounded to the nearest integer value and Clopper-Pearson CIs will be calculated using the exact weight-adjusted values using the Beta distribution. If all observed cases are positive the number of events will be set to N_1 and N_2 and these values will be used to calculate the confidence intervals.

If insufficient non-missing data are collected in participants with 1 trial vaccination the vaccine groups will be pooled to give the following vaccine options:

- Placebo vaccinations only (t_1)
- At least one HIL-214 vaccination (t_2)

The above formulae will be adjusted accordingly.

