9.1.1.3 Analysis Methods

A primary immunogenicity estimand and a supplementary estimand will be created for all of the endpoints outlined in **Table 8**. Analyses will be completed for the subgroups defined in **Section 7.4**.

For the primary immunogenicity estimands a complete case analysis will be performed, meaning any subjects with missing data for the parameter of interest will be excluded from the analysis.

For the supplementary immunogenicity estimands for the primary endpoints the missing data will be accounted for by reweighting the estimates using the method of inverse probability weighting. See **Section 7.5.1** for more details.

For the binary primary immunogenicity endpoints a standard summary for the categorical outcome will be presented as well as descriptive statistics for the continuous values. Further, the difference in percentage of subjects in the vaccine group with the event and the percentage of subjects in the

placebo group with the event will be evaluated. This will be presented along with a 95% CI calculated using the Miettinen and Nurminen [2] method as shown in **Section 5.4.1**.

For all continuous primary immunogenicity endpoints the geometric mean titer/concentration (GMT/GMC) with 95% CIs and geometric standard deviation (GSD) will be calculated. The GMRs between the vaccine group and the placebo group along with a 95% CI will be calculated using the analysis of variance (ANOVA) model with natural logarithm of antibody titer/concentration as the response variable and trial arm as a factor. Where country is used as a covariate (see **Section 7.3**) the adjusted GMs will also be presented. Further details can be found in **Section 5.4.3**.

For all primary immunogenicity parameters a reverse cumulative distribution curve will be produced, with titer/concentration on the x-axis and the percentage of patients below the titer value on the y-axis. All graphs will contain the two vaccine groups which will be overlaid.

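### When every observed infant in both arms is above the threshold, the supplementary analysis gives a difference of 0 with no confidence interval for it, although a valid score interval exists (minor)

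*SAP*

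**What the plan says.** SAP 9.1.1.3 creates a primary and a supplementary estimand for every primary endpoint. "For the supplementary immunogenicity estimands for the primary endpoints the missing data will be accounted for by reweighting the estimates" by inverse probability weighting, with details in SAP 7.5.1. That section has two rules for the case where everyone observed is positive. On the estimate: "If all observed cases are positive in both vaccine groups, then the difference will be set to 0". On its precision: "If all observed cases are positive in both vaccine groups confidence intervals will not be calculated". It keeps Clopper-Pearson intervals for each arm, with the event counts set to the analysis-set sizes.

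SAP 5.4.1, which governs the primary complete-case analysis, has no such exception: "The 95% confidence intervals for the differences in percentages will be computed using the Miettinen and Nurminen (MN) [2] method". The equation printed there, and repeated with weighted quantities in 7.5.1, uses restricted proportions that "are the maximum likelihood estimators for" the two arm rates under a null difference of zero.

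Protocol 13.1.2 assesses the primary objective through 95% intervals for differences and geometric mean ratios. The seven threshold endpoints (diphtheria, tetanus, polio types 1 to 3, PRP and HBsAg) all belong to the hexavalent vaccines, which SAP 7.4 analyses by country only.

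**The concern.** In a descriptive trial the interval is the planned statement of how large a between-arm difference the data leave open. SAP 9.1.1.3 promises one with each difference in percentages. Under the 7.5.1 rule, that statement is missing from the treatment-policy result exactly when the estimate is 0. A 0 from 50 infants per arm and a 0 from 150 per arm would be reported alike for the difference, although they differ in precision by a factor of nearly three.

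**Working it through.** **Inputs**
- z = 1.960, z² = 3.8415: "two-sided 95% confidence intervals" (SAP 5.4.1).
- λ = (n₁+n₂)/(n₁+n₂−1) (SAP 5.4.1).
- Total size: "The planned number of subjects is approximately 400, with 200 receiving HIL-214 and routine childhood vaccines and 200 receiving Placebo" (SAP Section 6); 1:1 allocation, stratified by country (SAP 5.2).
- US enrolment: at least 100 (Protocol 4.2). This is a floor, so 50 per arm is an assumption. If the US had exactly 100, Panama would have (400 − 100)/2 = 150 per arm.
- Expected response rates: none given.

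**Step 1. The plan's 0.** With all observed infants positive, Eᵢ = nᵢ. If the weights are fitted to the set being analysed, wᵢ = Nᵢ/nᵢ. Each weighted proportion is then ΣNᵢ/N = 1, and the difference is 0. The plan's value is reproduced.

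The weight model has no country term. With weights pooled over countries, the by-country proportions can miss 1. In an invented example, placebo is (2×10/6 + 44×190/180)/50 = 0.996 and HIL-214 is (2×12/9 + 45×188/170)/50 = 1.049. Fixing the difference at 0 avoids that artefact.

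**Step 2. The printed equation.** Under a zero difference both restricted proportions equal 1, so p̃(1 − p̃) = 0 and the half-width is exactly 0.

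**Step 3. The score interval.** The cited method re-estimates the restricted proportions at each candidate difference. At −d the likelihood is p₁^n₁ (p₁ − d)^n₂, which increases in p₁, so p̃₁ = 1 and p̃₂ = 1 − d. The lower limit solves

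d² = z²λ d(1 − d)/n₂, which gives d = z²λ/(n₂ + z²λ).

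The upper limit has the same form with n₁. At 50 per arm: λ = 100/99 = 1.0101, z²λ = 3.8803, d = 3.8803/53.8803 = 0.0720.

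| Sampled per arm | 95% limits (points) |
|---|---|
| 40 | ±8.86 |
| 50 | ±7.20 |
| 60 | ±6.06 |
| 75 | ±4.90 |
| 100 | ±3.72 |
| 150 | ±2.51 |

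Numerical inversion of the restricted likelihood gives the same values at 40, 50, 75 and 150. The Newcombe interval is ±7.13 at 50 and ±2.50 at 150.

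**Step 4. Next to the boundary.** Take HIL-214 49/50 and placebo 50/50, a difference of −2 points. The printed equation has p̃ = 99/100 and half-width 1.96 × √[(100/99) × 2 × 0.99 × 0.01/50] = 3.9 points, so −5.9 to 1.9. Score inversion gives −10.6 to 5.3.

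**Step 5. How often the case arises.** With a common true rate p and 50 sampled per arm, the chance that all are positive is p¹⁰⁰: 0.6% at 95%, 13% at 98%, 37% at 99% and 61% at 99.5%. At 150 per arm it is p³⁰⁰, about 5% at 99%. These rates are assumptions.

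**The case against.** The strongest reply is that little is lost. The primary set (all doses in window) is nested in the supplementary set (at least one trial dose in window; SAP 7.1 and 7.2). If every observed infant in the larger set is positive, so is every one in the smaller. The primary table then shows the same 0, with a Miettinen-Nurminen interval called for. Per-arm Clopper-Pearson intervals also stand beside the supplementary 0; at 50/50 the lower limit is 92.9%. Neither document states a non-inferiority margin, so no decision turns on the missing interval.

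Most of this stands, and it makes the point minor. It does not remove it. Per-arm intervals do not bound the difference. Because they use the full analysis-set sizes, they also count unsampled infants as positive: with 40 of 50 sampled, the lower limit shown would be 92.9% where the sampled infants support 91.2%. The supplementary estimand also has its own promised interval. And the primary interval is secure only if it is programmed as the cited method, since the equation printed in 5.4.1 collapses to zero width here.

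The rule may itself be a workaround for that collapse. If so, the equation is what needs correcting.

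**Conclusion.** The point holds as a minor reporting gap in a boundary case of a supplementary, descriptive analysis. The difference of 0 is correct; what is missing is its interval, which exists and is about ±7.2 points at 50 sampled per arm, ±4.9 at 75, ±3.7 at 100 and ±2.5 at 150. These figures assume equal arms, and sizes that the documents do not fix.

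A reader might infer more, and the documents do not support it:
- That the output would carry no measure of uncertainty, or would pass as proof of no interference. Per-arm intervals are kept, and the primary analysis has no such exception.
- That the US interval is 7 points. The documents give only a minimum for US enrolment, so 7.2 applies at that floor with every infant sampled.
- That the case is likely for several endpoints. No response rates are given, and the chance runs from under 1% to about 61% over the assumed rates above.
- That an interval at 200 per arm is relevant. These endpoints are analysed by country only.

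**What to change.** Replace the sentence in SAP 7.5.1 with, for example: *Where every observed infant in both arms is above the threshold, the difference is 0 and its 95% CI is the Miettinen-Nurminen score interval computed from the unweighted numbers of infants sampled per arm.* Sampled numbers matter here: analysis-set sizes would credit information from infants without a result (40 sampled of 50 would show ±7.2 where ±8.9 is supported).

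In 5.4.1 and 7.5.1, state that the limits come from score inversion, with the restricted maximum likelihood estimates recomputed at each candidate difference. Without this, deleting the sentence would produce an interval from 0 to 0.

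Report the interval in the supplementary table, and in any supplementary forest plot that is produced; SAP 9.1.1.3 does not say whether its forest plots cover the supplementary estimands.

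The cost is a short SAP edit and a standard procedure call, checked against the closed form above because some routines fail numerically at this boundary. Data collection is unchanged. The output looks slightly less favourable.

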7.5.2 Partial Dates/Times

Partial dates and times for AEs, medical conditions and concomitant medications will be imputed for the purpose of assigning study phases and calculating duration. Imputed dates and times should not be shown in the listings.

Partial AE onset and concomitant medication start dates will be imputed as follows:

- If only the month and year are specified, and the month and year of either trial vaccination are not the same as the month and year of the start date, then use the 1st of the month or the date of birth, whichever is latest.
- If only the month and year are specified, then set to the date of the latest vaccine received in the same month and year. If this results in a start date after a known or partial end date, then use the 1st of the month.
- If only the year is specified, and the year of either trial vaccination is not the same as the year of the start date, then use January 1st of the year of the start date or the date of birth, whichever is latest.
- If only the year is specified, then set to the date of the latest trial vaccine received in the same year. If this results in a date that is after the known end date of the AE/medication then use the date of the earliest trial vaccination or January the 1st, whichever is the latest.

If the start date is completely unknown, then use the date of the last trial vaccination. If this results in a date that is after the known end date of the AE/medication then use the date of the earliest trial vaccination. If this results in a start date after a known or partial end date, do not impute the start date.

Imputation of partial AE start times:

- If the actual or imputed start date is the same as the date of a trial vaccination and the start time is completely missing, then use the time of the corresponding trial vaccination.
- If the actual or imputed start date is not the same as any trial vaccine administration, and the start time is completely missing, then use 00:00.
- If the actual or imputed start date is the same as any trial vaccine administration, and the start time is partially missing (hh:XX) then use the following:
 - If the hour is the same as the hour of the any trial vaccine administration time then use the complete time of trial vaccine administration (i.e., both hours and minutes)
 - If the hour is not the same as the hour of the start time than use hh:00.
- If the actual or imputed start date is not the same as the trial vaccine administration, and the start time is partially missing (hh:XX) then use hh:00.

Partial medical conditions start dates will be imputed as follows:

- If only the month and year are specified, then use the 1st day of the month or the date of birth, whichever is latest.
- If only the year is specified, then use January 1st of that year or the date of birth, whichever is latest.
- If the start date is completely unknown, do not impute the start date.

Partial AE resolution, medical condition stop dates and concomitant medication stop dates will be imputed as follows:

- If the event, condition or medication is flagged as ongoing, do not impute the stop date.
- If only the month and year are specified, then use the last day of the month or the date of data-cut, whichever is earliest.
- If only the year is specified, then use December 31st of that year or the date of data-cut, whichever is earliest.
- If the stop date is completely unknown, do not impute the stop date.

Partial AE resolution and concomitant medication stop times will be imputed as follows:

- If the actual or imputed stop date is non-missing, and the stop time is completely missing, then use 23:59 on that date.
- If the actual or imputed stop date is non-missing, and the stop time is partially missing, then hh:59 for missing minutes.
- If the actual or imputed stop date is missing, do not impute the stop time.

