9.1.8 Safety Assessments

Safety assessments will begin at Visit 1 for MAAEs, SAEs, and AEs leading to withdrawal from the trial.

Safety assessments by site staff are planned immediately following each dose of trial vaccine. In addition, the subject's LAR will collect solicited local and systemic reactions daily for the 7 days (including day of administration) post-dose 1 (when the subject is aged 4 months) and dose 2 (when the subject is aged 6 months) of the trial vaccine via eDiary.

Safety assessments will also be made when the subject returns to the clinic for the second dose of trial vaccine (Visit 3), when the subject is aged 6 months, then at Visit 4 and Visit 5 (whether subject is aged ~7 months and 12 months, respectively). These assessments will include collection and recording of unsolicited AEs (serious and non-serious), withdrawal from trial vaccine (Visit 2 and Visit 3), withdrawal from trial, SAEs and MAAEs.

Refer to Section 10.1 for safety definitions. Details on collection and reporting of AEs are in Section 10.5.

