8.5 Prior and Concomitant Medications

Prior medication definition: If a subject takes a medication before Visit 2, this medication will be classified as 'prior medication'. With this definition, any medication recorded that has been taken for at least 1 day and has been stopped before Visit 2 will be considered as prior.

Concomitant medication definition: Prior medication not stopped before Visit 2 will be classified as 'concomitant medication'. Medication will be labelled as 'concomitant medication' when the start date is between Visit 2 and the final study visit (Visit 5) or, in case of early termination, on the date of the subject's last visit. With this definition, any medication that has been taken for at least 1 day between Visit 2 and Visit 5 will be considered as concomitant.

Medications will be coded according to the 2020 version of the World Health Organization Drug Dictionary (WHODD). Medical procedures will not be coded. Prior and concomitant medications will be listed for the randomized analysis set by trial vaccine group. Concomitant medications will be summarised.

Procedure history will be listed separately by the procedure reported term for the randomized analysis set by trial vaccine group. Concomitant medical procedures carried out during the study will be listed for the randomized analysis set.

9 Immunogenicity Analyses

All immunogenicity variables will be listed by subject within study center. Data will be summarised by trial vaccine group and country.

For all continuous immunogenicity variables a standard summary of the number of subjects with an assessment (n), geometric mean (with 95% CI), geometric standard deviation, median, Q1, Q3, minimum and maximum will be presented alongside the number of assessments below the LLOQ and LLOD and above the ULOQ. The number of subjects missing an assessment will also be summarized.

For categorical variables the count and percentage of subjects with antibody titers/concentrations over a pre-defined threshold, count and percentage of subjects achieving seroresponse to HIL-214, and 95% CIs for the percentages, computed using the exact Clopper-Pearson [1] method, will be presented.

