10.2.4 Unsolicited Adverse Events

Unsolicited AEs will be collected up to 28 days after administration of each dose of trial vaccine (including the day of administration). Only unsolicited AEs recorded after the first dose of trial vaccine will be summarised. All AEs will be listed with the timing relative to the first dose indicated.

Any unsolicited AE will be summarized in the following 3 time intervals after each trial vaccine dose visit (Visit 2 and Visit 3):

- 1) Overall up to 28 days after each dose (including the day of administration)
- 2) With onset between 1 and 7 days after each dose (including the day of administration)
- 3) With onset between 8 and 28 days after dose (including the day of administration)

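### The year-only start-date rule in SAP 7.5.2 has no final check against the end date, so a record that ended before dose 1 is given a start at dose 1, after its own end.

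*SAP*

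**What the plan says.** SAP 7.5.2 states that partial dates "will be imputed for the purpose of assigning study phases and calculating duration". An imputed start therefore decides whether a record counts as before or after vaccination.

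The rules for AE and medication start dates differ in how they end:

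- **Month and year known, dose in that month.** Use the latest vaccine date in that month. Final check: "If this results in a start date after a known or partial end date, then use the 1st of the month".
- **Year only, no dose in that year.** Use 1 January or the date of birth, whichever is later.
- **Year only, dose in that year.** "If only the year is specified, then set to the date of the latest trial vaccine received in the same year". If that is after the known end date, "use the date of the earliest trial vaccination or January the 1st, whichever is the latest". There is no final check.
- **Start completely unknown.** Use the last dose, then the earliest dose if the last is after the known end. Final check: "If this results in a start date after a known or partial end date, do not impute the start date".

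The same section sets a completely missing AE start time on a vaccination date to the time of that vaccination. It also says that imputed dates should not appear in listings.

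Downstream, SAP 10.2.4 states: "Only unsolicited AEs recorded after the first dose of trial vaccine will be summarised". It sets no condition on the end date. SAP 8.5 classes a drug stopped before Visit 2 as prior, but also says: "Medication will be labelled as 'concomitant medication' when the start date is between Visit 2 and the final study visit".

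**The concern.** The year-only fallback looks as if it chooses between two dates. When dose 1 is in the named year, it does not: dose 1 cannot precede 1 January of its own year, so the later of the two is always dose 1. The 1 January option matters only when dose 1 fell in the year before the named one. A record that was over before dose 1 is therefore dated to dose 1, and nothing afterwards compares that date with the end.

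A record with less information is treated more safely: if the start is completely unknown, the same end date leaves it unimputed. This points to an omission and not a deliberate choice.

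What is at stake is false post-dose events in the safety tables, impossible durations and an ambiguous drug label. Because imputed dates are kept out of the listings, a reader of the report could not easily see the cause.

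**Working it through.** The documents give no figure to reproduce. The check applies the rule as written.

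**Inputs.** The rules are those of SAP 7.5.2. Calendar dates are assumed: birth 1 May 2023, dose 1 on 1 September 2023, dose 2 on 1 November 2023, start recorded as 2023. Duration is taken as end − start + 1. This is also an assumption, matching the relative-day convention of SAP 5.3.1.2.

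**Known end dates.** Step 1 gives 1 November. If that is after the end, step 2 gives max(1 September, 1 January) = 1 September.

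| End date | Imputed start | Duration (days) | Completely-unknown rule |
|---|---|---|---|
| 20 Jul 2023 | 1 Sep 2023 | −43 + 1 = −42 | not imputed |
| 31 Aug 2023 | 1 Sep 2023 | −1 + 1 = 0 | not imputed |
| 1 Oct 2023 | 1 Sep 2023 | 30 + 1 = 31 | 1 Sep 2023 |
| 1 Dec 2023 | 1 Nov 2023 | 30 + 1 = 31 | 1 Nov 2023 |

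In the first two rows the relative day is 1 Sep − 1 Sep + 1 = 1, so an AE falls in both the 1–7 day and the 28-day interval of SAP 10.2.4.

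**Other calendars.** The rule was run with dose 1 on each day from 1 July 2023 to 30 June 2024, dose 2 61 days later, Visit 1 61 days before dose 1, and every end date from Visit 1 to 28 days after dose 2. The named year was that of the end date.

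- End before dose 1 and dose 1 in the named year: the start is after the end in all 20,435 combinations (16,714 with both doses in one year, 3,721 with doses in two years).
- All other combinations: none.

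These counts confirm the logic. They are not rates of affected records.

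**Partial end dates.** The year-only fallback is triggered by a known end date only, whereas the final checks of the two neighbouring rules say known or partial. Suppose the end is recorded as July 2023, which 7.5.2 completes to 31 July. If a partial date does not count as known, the start stays at 1 November: duration −93 + 1 = −92 days, placed after dose 2.

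**The 'either ... not the same' conditions.** Visits 2 and 3 are 2 months ± 7 days apart, with a month of 30.4375 days (protocol 2.2). The minimum gap is 2 × 30.4375 − 7 = 53.875, so at least 54 days. Two doses in window never share a calendar month, so for a subject with both doses one of them is always in another month. Read literally, the first month condition is then always met and the rule for a dose in the same month is never reached. For the year, the literal condition is met only when the doses fall in different years. That would send the 3,721 two-year combinations to 1 January or date of birth, but all 16,714 same-year combinations would still fail.

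**The case against.** The strongest reply is that hardly any record will meet the rule. Protocol 9.1.2 sends adverse occurrences between consent and the first trial vaccine to the medical history page, except those related to a screening procedure. Medical-history dates have their own rule, without this gap. Protocol 12.1 provides logic checks for inconsistent and missing dates, with queries to the site. A year-only onset with a full end date, in an infant seen at about 2 and 4 months of age, is just what those checks should catch.

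This stands as a limit on size. It does not remove the gap. Protocol 9.1.8 says: "Safety assessments will begin at Visit 1 for MAAEs, SAEs, and AEs leading to withdrawal from the trial". Protocol 10.4.4 collects SAEs from consent, the schedule of procedures collects unsolicited AEs for 28 days after each routine vaccine, and protocol 9.1.2 records medications as concomitant from Visit 1. The imputation rule exists for dates that queries fail to complete.

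A second reply concerns drugs. SAP 8.5 says that a drug stopped before Visit 2 is prior, and that a concomitant drug is one taken for at least one day between Visit 2 and Visit 5. A reader might infer that the drug is simply treated as post-vaccination. The text does not go that far: only the start-date sentence points that way. Concomitant medication use is handled by treatment policy in every estimand, so the label moves no data.

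**Conclusion.** The defect holds, as a small one. For a year-only start, with dose 1 in the named year and a known end before dose 1, the rule always gives a start after the end. An affected AE becomes a day-1 event after dose 1 with a zero or negative duration. An affected drug gets two conflicting labels. The primary and secondary immunogenicity analyses are not affected.

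The result does not depend on the assumed calendar, only on the end preceding dose 1 within the named year. If 'either' is read literally, it is confined to subjects whose doses fall in one year.

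Three stronger readings are not supported:

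- A reader might want a percentage of pre-dose records that are misdated. Any such figure would depend on assumed distributions of onset, end and visit dates and on the reading of 'either'. The documents give neither these distributions nor a count of year-only records.
- A reader might conclude that 'either ... not the same' is always true in both rules. That is so for the month rule in subjects with both doses, but not for the year rule.
- A reader might infer that the safety comparison as a whole is unreliable. With few records exposed, nothing in the documents supports that.

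**What to change.** 1. Extend the year-only rule with the safeguard that the completely-unknown rule already has ("If this results in a start date after a known or partial end date, do not impute the start date"), and add that such a record is assigned to the pre-vaccination period. The added clause matters because an unimputed start does not by itself place the record in a period. Make the existing fallback test known or partial end dates too.
2. An alternative is 1 January or the date of birth, whichever is later, for phase assignment only. It should not be used for duration: in the example ending 20 July 2023 it gives a start of 1 May 2023, before Visit 1, and a duration of 80 + 1 = 81 days.
3. In the two 'either ... not the same' conditions, write that neither trial vaccination is in that month, or in that year.
4. In SAP 8.5, state that a drug stopped before Visit 2 is prior whatever its imputed start.

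The cost is a few sentences and a small change to the derivation code, best made before unblinding. Records with an end on or after dose 1 keep their dates under item 1 when the end date is known. Item 3 changes dates only if the conditions had been programmed literally.
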